9.2 Sample Size estimate

Each patient will have measurements of Dice similarity coefficients for both invasive and noninvasive approaches. A previous study²¹ showed that the mean for Dice similarity coefficient of the AVM nidus between CTA and MRI was 0.765 and the standard deviation was 0.0894. A sample size of 14 patients achieves 92% power to detect non-inferiority using a one-sided t-test with a significance level of 0.05 when the margin of non-inferiority is -0.077 (10% margin) and the true difference between the mean of invasive approach and non-invasive approach is 0.0. Sample size was estimated using a non-inferiority test for one mean in PASS 14 software.

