6.1.1 Definitions

Target: Target is the AVM nidus (figure 1) excluding the feeding artery and draining vein or hemangioma, if present.

Reference Target lesion: AVM nidus identified using interventional cerebral arteriography superimposed to MRI of brain +/- CT angiography (CTA), per treatment team discretion that is used in the actual SRS treatment.

CTA Target lesion: AVM nidus identified using CT angiogram of the brain alone, at a later date (greater than one month later) in a blinded manner, by the Neurosurgeon who contoured the reference target lesion.

MRI Target lesion: AVM nidus identified using MRI of the brain alone, at a later date (greater than one month later) in a blinded manner, by the Neurosurgeon who contoured the reference target lesion.

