6.1.2 Evaluation and comparison of targets

Two methods of segmentation geometric accuracy evaluation, Dice coefficients and Hausdorff distance analysis, will be utilized to compare the reference target generated from interventional cerebral arteriography to targets generated from CT angiograms.

6.1.2.1 Dice Coefficients (DCs = $2(A \cap B) / (A + B)$), where A and B are the ground-truth and evaluated as segmented volumes, respectively. Dice coefficient is a simple spatial overlap index and a reproducibility validation metric¹⁶ and a reproducibility validation metric, which has been adopted to validate the segmentation of white matter lesions in MRI¹⁷ and brain tumors¹⁸. The value of a Dice Coefficients ranges from 0, indicating no spatial overlap between two sets of images, to 1, indicating complete overlap.

6.1.2.2 Hausdorff distance (HD) between two finite point sets A and B is defined by $HD(A, B) = \max(h(A, B), h(B, A))$, where $h(A, B) = \max_{a \in A} \min_{b \in B} \|a - b\|$. Spatial distance based metric, such as HD, is widely used in the evaluation of image segmentation when the segmentation overall accuracy, such as the boundary delineation (contour), of the segmentation is of importance¹⁹.

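### The powered test in section 9.2 compares CTA with an invasive Dice mean that the design does not produce, and no limit for CTA-versus-reference agreement is stated

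*Combined protocol and SAP*

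**What the plan says.** Section 9.2 states that "Each patient will have measurements of Dice similarity coefficients for both invasive and noninvasive approaches". Its planning figures come from a cited study in which the "mean for Dice similarity coefficient of the AVM nidus between CTA and MRI was 0.765 and the standard deviation was 0.0894". With 14 patients, a one-sided t-test at 0.05 and a margin of −0.077, described as 10%, it claims 92% power when "the true difference between the mean of invasive approach and non-invasive approach is 0.0". It adds: "Sample size was estimated using a non-inferiority test for one mean in PASS 14 software".

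Section 6.1.1 defines three contours per patient:

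- the reference target, "AVM nidus identified using interventional cerebral arteriography superimposed to MRI of brain +/- CT angiography (CTA), per treatment team discretion", which is the one used for treatment;
- the CTA target, "AVM nidus identified using CT angiogram of the brain alone", drawn more than a month later, blinded, by the same neurosurgeon;
- an MRI-alone target, drawn in the same way.

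Section 6.1.2 defines Dice as an overlap of A and B, "where A and B are the ground-truth and evaluated as segmented volumes, respectively", and applies it to the reference target against the CTA target.

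Sections 2.3 and 9.1 give the primary endpoint as a comparison of the reference with both CTA and MRI-alone targets, to judge non-inferiority to the institution's standard. Section 9.3 covers interim reports only and contains no primary test.

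**The concern.** A Dice coefficient belongs to a pair of contours. Here the invasive contour is one member of the pair, the ground truth, so it has no Dice of its own to be averaged and compared with the CTA mean. The hypothesis in 9.2 needs a quantity that the study will not have.

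An analyst would have to supply the comparator, possibly after seeing the Dice values. The claim at stake is the primary one: section 1.3 says that adequate CTA targets may lead future investigators to omit arteriography selectively. Patient safety is not affected by this point, because treatment follows the reference target.

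**Working it through.** **Inputs (section 9.2):** n = 14, one-sided alpha 0.05, margin 0.077, SD 0.0894, published mean 0.765, true difference 0.

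**Step 1. Reproduce the 92%.** For a one-mean t-test:

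- Standard error = 0.0894/√14 = 0.02389.
- Noncentrality = 0.077/0.02389 = 3.22, with 13 df and critical t = 1.771.
- Power = P(noncentral t > 1.771) = 0.9198.

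This matches the stated 92%.

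**Step 2. Look for the second mean.** Section 6.1.1 gives one reference, one CTA and one MRI-alone contour per patient. The possible pairs are CTA–reference, MRI–reference and CTA–MRI. None is a Dice for the invasive approach, because there is no repeat or second-reader arteriography contour. Pairing the reference with itself gives 1.0. The limit would then be 1.0 − 0.077 = 0.923, and power at a true CTA mean of 0.765 would be practically zero.

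**Step 3. Suppose two Dice values per patient did exist.** A paired t-test is a one-mean test on the differences. If each value has SD 0.0894, the SD of the difference is 0.0894 × √(2(1 − ρ)), where ρ is the within-patient correlation.

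| ρ (assumed) | SD of difference | Power, n = 14 |
|---|---|---|
| 0 | 0.1264 | 70% |
| 0.25 | 0.1095 | 80% |
| 0.5 | 0.0894 | 92% |
| 0.75 | 0.0632 | 99.6% |

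On this reading 92% requires ρ = 0.5, which 9.2 does not state.

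**Step 4. Suppose a fixed benchmark of 0.765 was meant.** Ten percent of 0.765 is 0.0765, which fits the stated margin. The limit is 0.765 − 0.077 = 0.688 (inferred; it appears nowhere in the documents). The lowest passing observed mean, if the observed SD is 0.0894, is 0.688 + 1.771 × 0.02389 = 0.730. Power depends on the true mean Dice against the reference, which the documents do not give:

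| True mean (assumed), SD 0.0894 | Power |
|---|---|
| 0.72 | 35% |
| 0.74 | 66% |
| 0.765 | 92% |
| 0.80 | 99.7% |

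**Step 5. Vary the SD.** The SD of CTA-versus-reference Dice is not given either. With the true mean 0.077 above the limit:

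| SD (assumed) | Power |
|---|---|
| 0.06 | 99.8% |
| 0.08 | 96% |
| 0.0894 | 92% |
| 0.11 | 80% |
| 0.12 | 74% |
| 0.15 | 57% |

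The assumed values in steps 3 to 5 only show how the figure moves; the documents do not support any one of them over another.

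**The case against.** The strongest reply is that the intention is clear. Section 9.2 gives the metric, test, alpha, margin, a mean of 0.765 and a one-mean procedure, so 0.688 can be worked out and the calculation is coherent. This is fair as far as it goes, and 0.688 is the best inference. But a primary success limit should not have to be inferred. Nor is 0.688 justified as acceptable overlap with arteriography: as 9.2 describes its source, it is derived from agreement between CTA and MRI.

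A reader might infer that 9.2 contradicts itself by describing two means and then using a one-mean procedure. The text does not support that. A paired comparison is a one-mean test, so the wording and the procedure can agree; what is missing is the invasive Dice.

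Another rescue is to compare Dice(CTA, reference) with Dice(MRI, reference). That does give two values per patient, but both approaches are non-invasive, so it does not fit 9.2.

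It is also fair to say that the cited study could not be checked. Its listed title concerns time-resolved 3D digital subtraction angiography, so the CTA-versus-MRI description may be loose. The mismatch stands on the plan's own words, but whether 0.0894 is a poor SD for CTA against the reference is unknown.

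Finally, this is a 14-patient feasibility study of imaging, not of therapy. That limits the consequences, but the plan still states a formal non-inferiority test with margin, alpha and power.

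**Conclusion.** The point holds. The primary test cannot be run as written, because no invasive Dice exists and no other section supplies a comparator or a limit. Even with the inferred limit of 0.688, a pass would show overlap relative to a figure described as CTA–MRI agreement, not non-inferiority to the arteriography standard.

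A reader might go further and conclude that the 92% is miscalculated or the study underpowered. The documents do not support either. The arithmetic is right (0.9198) for a true mean 0.077 above the limit with SD 0.0894. Power for the real question is unknown in both directions, since neither the mean nor the SD of CTA-versus-reference Dice is given.

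The undefined comparison and the unstated, unjustified limit need correcting before the analysis. The roles of MRI-alone and Hausdorff distance are lesser matters that the same amendment can settle. The conclusion takes 0.765 and 0.0894 as 9.2 describes them.

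**What to change.** 1. **Section 9.2, hypothesis.** Delete the sentence giving both approaches a Dice and the zero-difference assumption. Define the primary value as Dice(CTA target, reference target), one per patient. Test H0: mean Dice ≤ D0 with a one-sample, one-sided t-test at 0.05. State D0 before the analysis and justify it as acceptable overlap with the reference. If 0.688 is intended, say so and justify it in those terms.
2. **Section 9.2, power.** Restate it conditionally: 14 patients give 92% power if the true mean Dice exceeds D0 by 0.077 and the SD is 0.0894, an assumption taken from CTA-versus-MRI agreement. A grid of other SDs is not needed in the protocol.
3. **Sections 2.3 and 9.1.** Replace the non-inferiority claim with mean agreement with the reference above D0, and report a two-sided 90% confidence interval for mean Dice (half-width about 1.771 × 0.02389 = 0.042 if the observed SD is 0.0894). Make clear that the one powered test is CTA against reference, with MRI-alone and Hausdorff distance secondary unless the sponsor states otherwise.
4. **Reference contours that used CTA.** Section 6.1.1 lets the treating team use CTA for the reference, so CTA may inform both contours in some patients, which could raise agreement. Record its use for each patient, and repeat the primary Dice summary in patients whose reference did not use CTA, as a sensitivity analysis.

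**Cost:** an amendment to wording and one recorded item per patient; no new patients or images. The sponsor accepts a more modest conclusion and a conditional power figure, and a justified D0 may leave power above or below 92%.

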9.3 Data Analysis Plans

Interim reports will be prepared every six months until 35 days after the last patient is enrolled. In general, the interim reports will contain information about patient accrual rate with projected completion dates of the trial, status of and compliance rate of target generation from CT angiogram and MRI alone per protocol, and the frequencies and severity of renal toxicity of the subjects.

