target volume. However, it had not been routinely done due to uncertain benefit in treatment planning and a concern for renal burden from additional intravenous (IV) contrast usage.

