5.2 Follow-up Procedures

This is not a treatment study, and the subject will not be followed for AVM outcome for the purpose of this study. Serum creatinine value will be checked 1 week (-3 days/+7 days) after the procedure and 1 month (+/- 10 days) after the procedure.

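### Renal safety is summarised only by toxicity counts and grades with an unclear denominator, and the creatinine change from baseline, available by schedule in every subject, has no planned summary

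*Combined protocol and SAP*

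**What the plan says.** Section 9.3 is the only section on data analysis. It describes what the interim reports will in general contain, and its one renal item is "the frequencies and severity of renal toxicity of the subjects". Neither 9.3 nor any other section plans a summary, estimate or interval for change in creatinine.

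The measurements are nevertheless scheduled. A creatinine value within 30 days of SRS is an eligibility requirement (3.1.2). After the procedure, section 5.2 states: "Serum creatinine value will be checked 1 week (-3 days/+7 days) after the procedure and 1 month (+/- 10 days) after the procedure". Sections 4.5 and 6.2 repeat this. In the Time and Events table (5.3), the footnote about exceeding the recommended contrast dose is attached to the adverse event row and not to the creatinine row.

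Adverse events are treated differently. Sections 4.3, 5.3 and 7.3.1 (including its follow-up paragraph) tie scheduled toxicity assessment, or kidney-specific follow-up, to having exceeded the recommended dose. The stopping rule in 7.5 refers to a rate of kidney injury above an expected level that is not stated. It covers injury occurring although the dose limit is respected, and also failure to keep to that limit consistently.

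**The concern.** Section 1.2 gives two reasons why CT angiography is not routine at the centre: uncertain planning benefit and "a concern for renal burden from additional intravenous (IV) contrast usage". Section 1.3 says that contrast nephropathy usually appears as a transient creatinine rise. The protocol therefore names a continuous marker and collects it in everyone with a baseline, but plans to report only counts and grades.

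Two things are at stake. First, counts in at most 14 people say little about the event rate, and a general upward shift in creatinine need not appear in them. Second, the counts may not cover the right people. Subjects who stay within the recommended dose are the ones the first limb of the stopping rule is about, yet they have no scheduled adverse event assessment. A creatinine summary covering everyone would fill that gap from data already scheduled.

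**Working it through.** **1. The plan's own figure.** Section 9.2 gives the inputs: "A sample size of 14 patients achieves 92% power to detect non-inferiority", "using a one-sided t-test with a significance level of 0.05", with "the standard deviation was 0.0894", "the margin of non-inferiority is -0.077 (10% margin" and "the true difference between the mean of invasive approach and non-invasive approach is 0.0".
- Standard error = 0.0894/√14 = 0.0239.
- Noncentrality = 0.077/0.0239 = 3.22, with 13 degrees of freedom and a one-sided 5% critical value of 1.771.
- Power from the noncentral t = 0.920, so the stated 92% reproduces.

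This is the only calculation behind n = 14, and it concerns the Dice coefficient. No figure is given for renal safety.

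**2. What the counts can show if all 14 subjects are in the denominator.**
- Zero events, one-sided 95% upper bound: 1 − 0.05^(1/14) = 19.3%.
- Zero events, two-sided 95% upper bound: 1 − 0.025^(1/14) = 23.2%.
- One event: 7.1%, exact 95% CI 0.2% to 33.9%.
- Two events: 14.3%, exact 95% CI 1.8% to 42.8%.
- Chance of seeing no event, (1 − p)^14: 0.95^14 = 49% at a true rate of 5%, and 0.90^14 = 23% at 10%. These rates are assumptions, because the documents state no kidney injury rate.

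**3. The denominator.** Set side by side:
- Section 5.3, footnote 3: adverse event assessment on day 0, at 1 week and at 1 month applies only above the recommended dose.
- Section 7.5: the first limb concerns kidney injury in subjects within that dose.
- Section 9.3: frequencies are reported for the subjects, without saying which.

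Section 1.3 says CT and conventional angiography can typically be done with under 100 cc of contrast, against quoted limits of 225 mL (adults) and 125 mL (ages 10 to 18). Even if 100 cc is read as applying to each procedure, a typical adult total is under 200 cc. Few adults may then have scheduled assessment. As an illustration only, zero events gives a one-sided upper bound of 1 − 0.05^(1/7) = 35% with 7 assessed subjects and 1 − 0.05^(1/4) = 53% with 4.

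**4. What the paired change can show.** Let d be the log of the ratio of follow-up to baseline creatinine.
- With 14 pairs, the 95% CI half-width is t(0.975, 13) × SD/√14 = 2.160/3.742 × SD = 0.577 SD of d.
- The SD is not in the documents. If it were 0.10, exp(0.0577) = 1.059; if 0.20, exp(0.1155) = 1.122. The upper limit would lie about 6% to 12% above the geometric mean ratio.
- Missing values widen the interval. With 10 pairs the half-width is 2.262/√10 = 0.715 SD.

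**5. Timing.** The 1-week window runs from day 7 − 3 = 4 to day 7 + 7 = 14. Section 1.3 puts the creatinine peak at 4–7 days, so a draw late in the window can miss it. The 1-month value can fall at about day 30 + 10 = 40, while interim reporting ends 35 days after the last enrolment. The last subjects' values may therefore fall outside every interim report.

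**The case against.** The strongest reply is that renal safety is neither an objective nor an endpoint (2.1 to 2.3, 9.1). This is a feasibility imaging study sized for Dice, and 9.3 describes a monitoring report. No final analysis of any endpoint is written, so the renal gap is part of a wider one. That stands, and it limits how much weight the point deserves.

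Some stronger readings are tempting, but the documents do not support them:
- That creatinine is collected and then ignored. It determines eligibility, and 7.3.1 counts a clinically significant laboratory finding as an adverse event. What is missing is a planned within-subject change.
- That the plan reduces creatinine to a yes/no event. Section 9.3 includes severity, and 7.3.1 gives five grades. Whether smaller rises go ungraded depends on CTCAE cut-points that the documents do not reproduce.
- That the trial will claim the added contrast is tolerated. No section plans such a statement.
- That the 19.3% bound set against a 6% to 12% interval measures information lost. One concerns an event rate and the other a mean ratio, and the second rests on an assumed SD.

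The limits of the remedy also stand. Every subject receives both contrast procedures and IV hydration, with no comparator, so a mean ratio cannot isolate CT angiography. The baseline may be 30 days old, the peak may be missed, and a mean can hide one large rise. A ratio near 1 could reassure falsely.

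**Conclusion.** The point holds as an inexpensive improvement to safety reporting, not as a fault in the primary analysis. The planned renal summary consists of counts and grades whose denominator is unclear. Even on the favourable assumption that all 14 subjects are counted, zero events is compatible with a rate of up to 19.3% (one-sided 95%) or 23.2% (two-sided). The paired creatinine change is scheduled in everyone and would estimate the mean log ratio to ±0.58 SD with 14 complete pairs. Its precision in creatinine units cannot be stated without an assumed SD.

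The most useful gain is coverage: a creatinine table would include subjects within the recommended dose, whom 7.5 refers to and 5.3 leaves without scheduled adverse event assessment. The conclusion does not depend on any assumed event rate or SD.

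**What to change.** - In 9.3, keep the toxicity counts and grades, state the denominator, and give an exact 95% CI beside each frequency.
- Reconcile 4.3, 5.3, 7.3.1 and 7.5 on which subjects are assessed for kidney injury, so that the denominator follows from the text. Which clinical rule applies is for the investigators to decide.
- In the interim and final reports, list for all subjects, whatever their contrast total, the 1-week and 1-month creatinine ratios to baseline. Give the largest ratio, and the geometric mean ratio with its 95% CI and number of pairs at each visit.
- State that the final report includes 1-month values obtained after interim reporting ends.
- Label the table as descriptive. Note that it reflects both contrast procedures plus hydration without a comparator, that the day 4 to 14 window can miss the peak, and that a mean ratio near 1 is not evidence of tolerability.

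The cost is one table and a few sentences, with no added visit, sample or patient. The small downside is the risk of over-reading an uncontrolled mean, which the label and the individual ratios are meant to contain.

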10.0 STUDY MANAGEMENT

10.1 Conflict of Interest

Any investigator who has a conflict of interest with this study (patent ownership, royalties, or financial gain greater than the minimum allowable by their institution, etc.) must have the conflict reviewed by the UTSW COI Committee and IRB according to UTSW Policy on Conflicts of Interest. All investigators will follow the University conflict of interest policy.

10.2 Institutional Review Board (IRB) Approval and Consent

It is expected that the IRB will have the proper representation and function in accordance with federally mandated regulations. The IRB must approve the consent form and protocol.

In obtaining and documenting informed consent, the investigator should comply with the applicable regulatory requirement(s), and should adhere to Good Clinical Practice (GCP) and to ethical principles that have their origin in the Declaration of Helsinki.

Before recruitment and enrollment onto this study, the subject will be given a full explanation of the study and will be given the opportunity to review the consent form. Each consent form must include all the relevant elements currently required by the FDA Regulations and local or state regulations. Once this essential information has been provided to the subject and the investigator is assured that the subject understands the

implications of participating in the study, the subject will be asked to give consent to participate in the study by signing an IRB-approved consent form.

Prior to a patient's participation in the trial, the written informed consent form should be signed and personally dated by the subject and by the person who conducted the informed consent discussion.

10.3 Required Documentation (for multi-site studies)

Not applicable for this protocol.

10.4 Registration Procedures

All subjects must be registered in Velos before enrollment to the study. Prior to enrollment, eligibility criteria must be confirmed with the study coordinator.

The first subject enrolled at UTSW will receive a number beginning with 101 and each patient enrolled thereafter will have a sequential ID number (i.e. 102, 103, 104).

Each newly consented subject should be numbered using the schema provided above. Upon registration, the registrar will assign the additional registration/randomization code according to the numbering schema outlined above, which should then be entered as the patient study ID in Velos upon updating the status to "enrolled".

10.5 Data Management and Monitoring/Auditing

REDCap is the UTSW SCCC institutional choice for the electronic data capture of case report forms for SCCC Investigator Initiated Trials. REDCap will be used for electronic case report forms in accordance with Simmons Comprehensive Cancer Center requirements, as appropriate for the project

Trial monitoring will be conducted no less than annually and refers to a regular interval review of trial related activity and documentation performed by the DOT and/or the CRO Multi-Center IIT Monitor. This review includes but is not limited to accuracy of case report forms, protocol compliance, timeliness and accuracy of Velos entries and AE/SAE management and reporting. Documentation of trial monitoring will be maintained along with other protocol related documents and will be reviewed during internal audit.

Toxicity reviews will be performed, via the interim reports, every 6 months until 35 days after the last patient is enrolled. These reviews will be documented by the study team and/or the UTSW Simmons Comprehensive Cancer Center (SCCC) Data Safety Monitoring Committee (DSMC).

The UTSW Simmons Comprehensive Cancer Center (SCCC) Data Safety Monitoring Committee (DSMC) is responsible for monitoring data quality and patient safety for all UTSW SCCC clinical trials. As part of that responsibility, the DSMC reviews all serious adverse events and UPIRSOs in real time as they are reported and reviews adverse events on a quarterly basis. The quality assurance activity for the Clinical Research Office provides for periodic auditing of clinical research documents to ensure data integrity and regulatory compliance. A copy of the DSMC plan is available upon request.

The SCCC DSMC meets quarterly and conducts annual comprehensive reviews of ongoing clinical trials, for which it serves as the DSMC of record. The Quality Assurance Coordinator (QAC) works as part of the DSMC to conduct regular audits based on the level of risk. Audit findings are reviewed at the next available DSMC meeting. In this way, frequency of DSMC monitoring is dependent upon the level of risk. Risk level is determined by the DSMC Chairman and a number of factors such as the phase of the

study; the type of investigational agent, device or intervention being studied; and monitoring required to ensure the safety of study subjects based on the associated risks of the study. Protocol-specific DSMC plans must be consistent with these principles.

